- Grade 3 hypertension controlled by medical therapy;
- O Grade 3 diarrhea that improves to Grade ≤2 within 72 hrs after medical management has been initiated;
- Grade 3 skin toxicity that resolves to Grade ≤1 in less than 7 days after medical management (eg, immunosuppressant treatment) has been initiated;
- Any Grade \geq 3 amylase or lipase abnormality that is not associated with symptoms or clinical manifestations of pancreatitis;
- Grade 3 endocrinopathies controlled with medical therapy;
- Tumor flare phenomenon defined as local pain, irritation, or rash localized at sites of known or suspected tumor.
- Non-hematologic Grade \geq 3 laboratory abnormality if medical intervention is required to treat the patient or the abnormality leads to hospitalization.
 - Single laboratory values out of normal range that are unlikely related to trial treatment according to the Investigator, do not have any clinical correlate, and resolve to Grade ≤1 within 7 days with adequate medical management are not to be considered DLTs;
- ALT or AST >3 x upper limit of normal (ULN) (if normal at baseline) or >3 x ULN and doubling the baseline (if > ULN at baseline) associated with bilirubin >2 x ULN

For part B (untreated disease cohorts), enrollment will open following the completion of the corresponding dose expansion cohort in part A (cohorts A1b and A2b), assuming that the corresponding cohort in part A meets its efficacy and safety criteria for success (\geq 3 complete responses and \leq 3 DLTs).

All cohorts in part B will have an early stopping rule if >2 patients at any point meet the criterion for a DLT.

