13.2 Sample Size, Accrual Rate and Study Duration

13.2.1 Determining RP2D

The Dose Escalation phase of this study follows a 3+3 design with 2 or 3 dose levels for each cohort to determine the RP2D for each drug combination being tested. The RP2D will be defined as the highest dose level for which there are no more than 1/6 DLTs observed.

The following table shows the probability of escalation under various true DLT rates. With this design there is 91% probability of dose escalation if the true rate of DLT is 10% and 8% probability of escalation if the true DLT rate is 60%.

True Rate of DLT	Probability of escalation
10%	0.91
20%	0.71
30%	0.49
40%	0.31
50%	0.17
60%	0.08

Dose Expansion

Once the RP2D is established for a given cohort/drug combination in the relapsed/refractory setting (part A), an additional 9 or 12 eligible patients will be treated at the RP2D, for a total of 15 patients treated at that dose level. Whether it is 9 or 12 is dependent on whether 6 or 3 patients were treated at that dose level to determine the RP2D, respectively. With 15 patients, the 90% confidence interval for DLT will be no wider than +/-23%.

A combination will be judged promising in terms of efficacy **in part A (relapsed/refractory setting)** if in addition to being tolerable 3 or more patients out of 15 obtain a CR (based on a null hypothesis of CRR 5% and alternative hypothesis of CRR 30% with 87% power and a 4% one sided type I error).

True but unknown CR rate	0.05	0.1	0.15	0.2	0.25	0.3
Prob of observing ≥ 3 CRs	0.04	0.18	0.40	0.60	0.76	0.87

In the **relapsed/refractory setting (part A)**, a particular combination (A1b, A2b, A3b) will be judged tolerably safe if 3 or fewer patients out of 15 experience a DLT (based on a null hypothesis for DLT rate of 40% and an alternative hypothesis of 10% with 94% power and a 9% one-sided type I error).

True but unknown prob. of excessive toxicity	0.05	0.1	0.15	0.2	0.25	0.3	0.35	0.4
Prob of observing ≤3 pts with excessive tox	0.99	0.94	0.82	0.65	0.46	0.30	0.15	0.09

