If a cohort in part A meets these efficacy and toxicity endpoints, it will open in cohort B in previously untreated FL patients. These cohorts will treat up to 15 patients each. A combination will be judged promising in terms of efficacy **in part B (previously untreated setting)** if in addition to being tolerable based on above criteria) if 6 or more patients out of 15 obtain a CR (based on a null hypothesis of CRR 20% and alternative hypothesis of CRR 50% with 85% power and a 6% one sided type I error).

True but unknown CR rate	0.2	0.25	0.3	0.35	0.4	0.5
Prob of observing \ge 6 CRs	0.06	0.15	0.28	0.44	0.60	0.85

In the **upfront setting (part B)**, a particular combination (B1, B2) will be judged safe if 2 or fewer patients out of 15 experience excessive toxicity as defined above (based on a null hypothesis for excessive toxicity rate of 35% and an alternative hypothesis of 10% with 82% power and a 6% one-sided type I error).

True but unknown prob. of excessive toxicity	0.05	0.1	0.15	0.2	0.25	0.3	0.35
Prob of observing ≤2 pts with excessive tox	0.96	0.82	0.60	0.40	0.24	0.13	0.06

Based on historical rates, anticipated accrual will be 24 months. The anticipated time to primary endpoint is 30 months, and to study completion 48 months.

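### Section 13.2.1 attaches 85% (Part B) and 87% (Part A) power to a rule that also requires tolerability; at 10% toxicity the full rule has about 69% in Part B and 82% to 85% in Part A

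*Combined protocol and SAP*

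**What the plan says.** In section 13.2.1, under Dose Expansion, a Part A combination is judged promising for efficacy "if in addition to being tolerable 3 or more patients out of 15 obtain a CR". The accompanying figures are a CR rate of 5% against 30%, 87% power and 4% one-sided type I error. For Part B the condition reads "if in addition to being tolerable based on above criteria) if 6 or more patients out of 15 obtain a CR". There the CR rate is 20% under the null and 50% under the alternative, and the plan presents the rule as one "with 85% power and a 6% one sided type I error". The table under each rule gives the probability of reaching the CR count.

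Safety has its own rules in the same section. Part A allows at most 3 of 15 patients with a DLT (40% against 10%, 94% power, 9% type I error). A Part B combination "will be judged safe if 2 or fewer patients out of 15 experience excessive toxicity as defined above"; the figures given for this rule are a toxicity rate of 35% against 10%, 82% power and 6% type I error.

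On cohort size, the plan says of Part B: "These cohorts will treat up to 15 patients each". Section 5.1 adds: "All cohorts in part B will have an early stopping rule if >2 patients at any point meet the criterion for a DLT". Section 5.1 also makes the opening of a Part B cohort depend on the matching Part A cohort meeting both its CR and its DLT criterion. No probability of meeting both criteria together is given anywhere.

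**The concern.** Power should describe the decision that will be taken. Here that decision has two conditions, and the power printed beside it covers one. A reader of the Part B sentence would expect a combination with a 50% CR rate to be passed over about 15% of the time. A cohort with a third DLT is closed and fails the safety rule, so it cannot be called promising however many CRs it has. The chance of passing over a combination that is good on both counts must therefore be larger.

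This matters because CR rate is a primary endpoint, the first study goal in section 1.1 is to identify combinations worth taking into phase 2, and the joint Part A rule also controls whether Part B opens.

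**Working it through.** **Inputs** (section 13.2.1): n = 15 per cohort. Part A: at least 3 CRs at a 30% CR rate, at most 3 DLTs at 10%. Part B: at least 6 CRs at a 50% CR rate, at most 2 patients with toxicity at 10%. I take excessive toxicity in Part B to mean a DLT, which agrees with the section 5.1 stopping rule.

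**Step 1. Reproduce the plan's figures** (exact binomial, n = 15).

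| Rule | At the alternative | At the null | Plan states |
|---|---|---|---|
| A, ≥3 CR | 0.873 (30%) | 0.036 (5%) | 87%, 4% |
| A, ≤3 DLT | 0.944 (10%) | 0.091 (40%) | 94%, 9% |
| B, ≥6 CR | 0.849 (50%) | 0.061 (20%) | 85%, 6% |
| B, ≤2 toxicity | 0.816 (10%) | 0.062 (35%) | 82%, 6% |

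All agree to rounding. The 87% and 85% are therefore probabilities for the CR count alone.

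**Step 2. Both conditions, CR and DLT independent.** Joint power = P(enough CRs) × P(few enough with toxicity).

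- Part B: 0.849 × 0.816 = 0.693
- Part A: 0.873 × 0.944 = 0.825

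The early stop does not change the Part B figure. A cohort stops exactly when it has a third DLT, which already fails the rule.

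The Part B miss rate is 1 − 0.693 = 0.307. It is made up of 1 − 0.816 = 0.184 that fail safety, plus 0.816 × (1 − 0.849) = 0.123 that pass safety but fall short on CRs.

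**Step 3. Dependence.** The documents give no CR/DLT correlation. Treat patients as independent of each other, and let the probability that one patient has both a CR and a DLT run from 0 to its maximum of 0.10. The multinomial then gives:

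| | No overlap | Independent | Maximum overlap |
|---|---|---|---|
| Part B | 0.719 | 0.693 | 0.672 |
| Part A | 0.832 | 0.825 | 0.818 |

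Whatever the dependence, joint power cannot exceed that of the safety rule, so at 10% toxicity Part B is below 0.816.

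**Step 4. Part B by true toxicity rate** (CR rate 50%, independence).

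| Toxicity | 2% | 5% | 10% | 15% | 20% |
|---|---|---|---|---|---|
| Joint power | 0.847 | 0.818 | 0.693 | 0.513 | 0.338 |

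**Step 5. Part A given that the dose level passed 3+3.** The 15 patients include the 3 or 6 from escalation. At a 10% DLT rate:

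- P(0 of 3) = 0.9³ = 0.729, then 12 more patients with at most 3 DLTs allowed: 0.974
- P(1 of 3, then 0 of 3) = 0.243 × 0.729 = 0.177, then 9 more with at most 2 further DLTs allowed: 0.947
- Given passage: (0.729 × 0.974 + 0.177 × 0.947) / (0.729 + 0.177) = 0.969
- Joint power: 0.969 × 0.873 = 0.846

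**Step 6. Type I error of the joint rule** (null CR rate, 10% toxicity).

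- Part A: 0.036 × 0.944 = 0.034
- Part B: 0.061 × 0.816 = 0.050

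**Step 7. Other reading of the Part B tolerability reference.** If the criteria referred to were Part A's limit of 3, Part B would have 0.849 × 0.944 = 0.802, still below 0.85.

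**The case against.** The strongest reply is that nothing is miscalculated or concealed. The sentences speak of promise in terms of efficacy, their hypotheses concern the CR rate only, and the tables beneath are labelled as probabilities of reaching the CR count. The safety rules have their own power and tables, so a reader can see that a Part B combination with 10% toxicity fails safety 18% of the time. Separate operating characteristics are a legitimate way to present an exploratory phase 1b trial, and all that is missing is the product of two printed numbers. A cohort closed for DLTs has also failed on safety, which is not a failure to detect efficacy. Finally, section 5.1 requires discussion with regulatory authorities before Part B opens, so the rule is not the only control.

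Most of this stands, and it narrows the point. It does not remove it: the text joins the two conditions into one decision, puts a power beside that decision, and gives no joint figure.

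Some stronger readings are tempting and are not supported:

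- **That 85% and 87% are arithmetic errors.** They reproduce exactly for the CR count.
- **That Part B can never exceed 82%.** The ceiling belongs to the 10% toxicity alternative. At 2% toxicity joint power is 0.847.
- **That joint power could lie anywhere in 67–82% (Part B) or 82–87% (Part A).** These are general bounds for two events with the given marginal probabilities. Fifteen independent patients cannot reach the upper ends (Step 3).
- **That false positives are inflated.** Requiring tolerability lowers the type I error.

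**Conclusion.** The point holds as a mismatch between the stated power and the rule it is attached to. It carries weight mainly in Part B: about 69% (67% to 72% under within-patient dependence) against the 85% printed, so a combination with a 50% CR rate and 10% toxicity is passed over about 31% of the time. This rests on the plan's 10% toxicity alternative, on at most 2 of 15 as the operative Part B limit, and, for the 69% itself, on independence of CR and DLT. The Part B safety rule and the section 5.1 stop at a third DLT both support that limit.

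In Part A the gap is small: about 82% unconditionally, or about 85% for a dose level that has passed 3+3, against 87%. Taken alone it would hardly need a comment. Nothing here shows that the sample size or the thresholds are wrong.

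**What to change.** In section 13.2.1:

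1. State that 87% (Part A) and 85% (Part B) are the power of the CR criterion alone.
2. Add the probability of meeting both criteria at the stated alternatives. Part B: about 69%, range 67–72%. Part A: about 82%, or about 85% given passage through 3+3. State the 10% toxicity rate and the independence assumption alongside. A short row by true toxicity rate for Part B (Step 4) would be useful.
3. Note that at 10% toxicity the joint type I error is about 5.0% (Part B) and 3.4% (Part A).
4. Make clear that the tolerability criteria referred to in the Part B efficacy sentence are the limit of 2 of 15 already given for Part B.

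The cost is a few sentences and a less favourable power figure for Part B. Sample size, thresholds and clinical rules do not change.

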13.3 Reporting and Exclusions

The primary analysis will be performed on all evaluable patients.

1	Symptoms, but ambulatory. Restricted in physically strenuous activity, but ambulatory and able to carry out work of a light or sedentary nature (e.g. , light housework, office work).	80	Normal activity with effort; some signs or symptoms of disease.	
		70	Cares for self, unable to carry on normal activity or to do active work.	
2	In bed <50% of the time. Ambulatory and capable of all self-care, but unable to carry out any work activities. Up and about more than 50% of waking hours.	60	Requires occasional assistance, but is able to care for most of his/her needs.	
		50	Requires considerable assistance and frequent medical care.	
3	In bed >50% of the time. Capable of only limited self-care, confined to bed or chair more than 50% of waking hours.	40	Disabled, requires special care and assistance.	
3		30	Severely disabled, hospitalization indicated. Death not imminent.	
4	100% bedridden. Completely disabled. Cannot carry on any self-care. Totally confined to bed or chair.	20	Very sick, hospitalization indicated. Death not imminent.	
		10	Moribund, fatal processes progressing rapidly.	
5	Dead.	0	Dead.	

APPENDIX B CAIRO-BISHOP CLINICAL TUMOR LYSIS SYNDROME DEFINITION AND GRADING

Complication	0	1	2	3	4	5
Creatinine	\leq 1.5xULN	1.5xULN	>1.5-	>3.0-	>6.0xULN	Death
			3.0xULN	6.0xULN		
Cardiac arrhythmia	None	Intervention not indicated	Nonurgent medical intervention indicated	Symptomati c and incompletely controlled medically or controlled with device	Life- threatening (eg arrhythmia associated with CHF, hypotension, syncope, shock)	Death
Seizure	None		One brief, generalized seizure well controlled by anticonvulsa nt or infrequent focal motor seizures not interfering with ADLs	Seizure in which consciousne ss is altered; poorly controlled seizure disorder; with breakthroug h generalized seizures despite medical intervention	Seizure of any kind which are prolonged, repetitive, or difficult to control (eg status eplipecticus, intractable epilepsy)	Death

Note: Tumor lysis syndrome is defined by laboratory tumor lysis syndrome (uric acid \geq 476µmol/L or 8mg/dL or a 25% increase from baseline; potassium \geq 6.0mmol/L or 6mg/L or a 25% increase from baseline; phosphorus \geq 1.45mmol/L or a 25% increase from baseline; calcium \leq 1.75mmol/L or a 25% decrease from baseline) and at least one clinical complication.

Increases in creatinine and seizures are considered a clinical complication if they are not deemed attributable to the therapeutic agent

APPENDIX C DF/HCC MULTI-CENTER DATA AND SAFETY MONITORING PLAN

1. INTRODUCTION

The Dana-Farber/Harvard Cancer Center Multi-Center Data and Safety Monitoring Plan (DF/HCC DSMP) outlines the procedures for conducting a DF/HCC Multi-Center research protocol. The DF/HCC DSMP serves as a reference for any sites external to DF/HCC that are participating in a DF/HCC clinical trial.

1.1 Purpose

To establish standards that will ensure that a Dana-Farber/Harvard Cancer Center Multi-Center protocol will comply with Federal Regulations, Health Insurance Portability and Accountability Act (HIPAA) requirements and applicable DF/HCC Standard Operating Procedures.

1.2 Multi-Center Data and Safety Monitoring Plan Definitions

DF/HCC Multi-Center Protocol: A research protocol in which one or more outside institutions are collaborating with Dana-Farber/Harvard Cancer Center where a DF/HCC investigator is the sponsor. DF/HCC includes Dana-Farber/Partners Cancer Care (DF/PCC) Network Clinical Trial Affiliates.

Lead Institution: One of the Dana-Farber/Harvard Cancer Center consortium members (Dana-Farber Cancer Institute (DFCI), Massachusetts General Hospital (MGH), Beth Israel Deaconess Medical Center (BIDMC), Boston Children's Hospital (BCH), Brigham and Women's Hospital (BWH) responsible for the coordination, development, submission, and approval of a protocol as well as its subsequent amendments per the DFCI IRB and applicable regulatory guidelines (CTEP, Food and Drug Administration (FDA), Office of Biotechnology Activities (OBA) etc.). The Lead Institution is typically the home of the DF/HCC Sponsor. The Lead Institution also typically serves as the Coordinating Center for the DF/HCC Multi-Center Protocol.

DF/HCC Sponsor: The person sponsoring the submitted Multi-Center protocol who takes responsibility for initiation, management and conduct of the protocol at all research locations. In applicable protocols, the DF/HCC Sponsor will serve as the single liaison with any regulatory agencies (i.e. the FDA). The DF/HCC Sponsor has ultimate authority over the protocol and is responsible for the conduct of the study at DF/HCC and all Participating Institutions. In most cases the DF/HCC Sponsor is the same person as the DF/HCC Overall Principal Investigator; however, both roles can be filled by two different people.

Participating Institution: An institution that is outside the DF/HCC and DF/PCC consortium that is collaborating with DF/HCC on a protocol where the sponsor is a DF/HCC Investigator. The Participating Institution acknowledges the DF/HCC Sponsor as having the ultimate authority and responsibility for the overall conduct of the study.

Coordinating Center: The entity (i.e. Lead Institution, Medical Monitor, Contract Research Organization (CRO), etc) that provides administrative support to the DF/HCC Sponsor in order

that he/she may fulfill the responsibilities outlined in the protocol document and DSMP, and as specified in applicable regulatory guidelines (i.e. CTEP Multi-Center Guidelines). In general, the Lead Institution is the Coordinating Center for the DF/HCC Multi-Center Protocol.

DF/HCC Office of Data Quality (ODQ): A group within DF/HCC responsible ensuring highquality standards are used for data collection and the ongoing management of clinical trials, auditing, and data and safety monitoring. ODQ also coordinates quality assurance efforts related to multi-center clinical research.

DF/HCC Clinical Trials Research Informatics Office (CTRIO): A group within DF/HCC responsible for providing a comprehensive data management platform for managing clinical trial data.

2. GENERAL ROLES AND RESPONSIBILITIES

For DF/HCC Multi-Center Protocols, the DF/HCC Sponsor, the Coordinating Center, and the Participating Institutions are expected to adhere to the following general responsibilities:

2.1 DF/HCC Sponsor

The DF/HCC Sponsor, **[name]**, **MD**, will accept responsibility for all aspects of conducting a DF/HCC Multi-Center protocol which includes but is not limited to:

- Oversee the coordination, development, submission, and approval of the protocol as well as subsequent amendments.
- Ensure that the investigators, study team members, and Participating Institutions are qualified and appropriately resourced to conduct the protocol.
- Include the Multi-Center Data and Safety Monitoring Plan as an appendix to the protocol.
- Ensure all Participating Institutions are using the correct version of the protocol.
- Ensure that each participating investigator and study team member receives adequate protocol training (and/or a Site Initiation Visit prior to enrolling participants) and throughout trial's conduct as needed.
- Ensure the protocol will be provided to each participating site in a language understandable to all applicable site personnel when English is not the primary language.
- Monitor progress and overall conduct of the study at all Participating Institutions.
- Ensure all DFCI Institutional Review Board (IRB), DF/HCC and other applicable (i.e. FDA) reporting requirements are met.
- Review data and maintain timely submission of data for study analysis.
- Act as the single liaison with the FDA (investigator-held IND trials) as applicable.
- Ensure compliance with all requirements as set forth in the Code of Federal Regulations, applicable DF/HCC requirements, HIPAA requirements, and the approved protocol.
- Commit to the provision that the protocol will not be rewritten or modified by anyone other than the DF/HCC Sponsor.
- Identify and qualify Participating Institutions and obtain accrual commitments prior to extending the protocol to that site.

• Monitor accrual and address Participating Institutions that are not meeting their accrual requirements.

2.2 Coordinating Center

The general responsibilities of the Coordinating Center may include but are not limited to:

- Assist in protocol development.
- Maintain FDA correspondence, as applicable.
- Review registration materials for eligibility and register participants from Participating Institutions in the DF/HCC clinical trial management system (CTMS).
- Distribute protocol and informed consent document updates to Participating Institutions as needed.
- Oversee the data collection process from Participating Institutions.
- Maintain documentation of Serious Adverse Event (SAE) reports and deviations/violation submitted by Participating Institutions and provide to the DF/HCC Sponsor for timely review and submission to the DFCI IRB, as necessary.
- Distribute serious adverse events reported to the DF/HCC Sponsor that fall under the DFCI IRB Adverse Event Reporting Policy to all Participating Institutions.
- Provide Participating Institutions with information regarding DF/HCC requirements that they will be expected to comply with.
- Carry out plan to monitor Participating Institutions either by on-site or remote monitoring.
- Maintain Regulatory documents of all Participating Institutions which includes but is not limited to the following: local IRB approvals/notifications from all Participating Institutions, confirmation of Federalwide Assurances (FWAs) for all sites, all SAE submissions, Screening Logs for all sites, IRB approved consents for all sites
- Conduct regular communications with all Participating Institutions (conference calls, emails, etc) and maintain documentation all relevant communications.

2.3 Participating Institution

Each Participating Institution is expected to comply with all applicable federal regulations and DF/HCC requirements, the protocol and HIPAA requirements.

The general responsibilities for each Participating Institution may include but are not limited to:

- Document the delegation of research specific activities to study personnel.
- Commit to the accrual of participants to the protocol.
- Submit protocol and/or amendments to their local IRB.
- Maintain regulatory files as per sponsor requirements.
- Provide the Coordinating Center with regulatory documents or source documents as requested.
- Participate in protocol training prior to enrolling participants and throughout the trial as required (i.e. teleconferences).
- Update Coordinating Center with research staff changes on a timely basis.
- Register participants through the Coordinating Center prior to beginning research related activities.

- Submit Serious Adverse Event (SAE) reports to local IRB per institutional requirements and to the Coordinating Center, in accordance with DF/HCC requirements. Submit protocol deviations and violations to local IRB per institutional requirements and to the DF/HCC Sponsor in accordance with DF/HCC requirements.
- Order, store and dispense investigational agents and/or other protocol mandated drugs per federal guidelines and protocol requirements.
- Have office space, office equipment, and internet access that meet HIPAA standards.
- Participate in any quality assurance activities and meet with monitors or auditors at the conclusion of a visit to review findings.
- Promptly provide follow-up and/or corrective action plans for any monitoring queries or audit findings.

